3.1.3 Treatment Period

The Treatment period will begin on the day of randomization (Day 1), which is to be within 28 days after the last dose of first-line systemic anti-cancer therapy or last day of local regional therapy, if applicable, and will continue until investigator-determined progressive disease (PD) (using RECIST v1.1), unacceptable toxicity, or 1 year after the first dose, whichever occurs first.

Subjects who meet eligibility criteria will be randomly assigned in a 1:1 ratio to receive one of the following centrally randomized treatments:

- Arm A: Placebo
- Arm B: CMB305

An interactive response technology (IRT) system will use the following stratification factors at the time of randomization:

- Disease status at screening: locally advanced unresectable (LAUR) vs metastatic
- Tumor response during screening: stable disease (SD)/partial response (PR) vs complete response (CR)/no evidence of disease (NED)
- Baseline presence of anti-NY-ESO-1 antibody (yes vs no)

Subjects who are randomly allocated to the placebo arm will not be permitted to cross-over to the CMB305-containing treatment arm at any time before study closure.

Tumor imaging assessments will be performed every 8 weeks after Day 1 and radiographic evidence of disease progression will be determined by the investigator using RECIST v1.1. Subjects with a global deterioration of health status requiring discontinuation of study treatment but without objective evidence of disease progression (symptomatic deterioration) will be considered as having PD for the purpose of determining PFS. Radiographic images (e.g., computed tomography [CT] scan or magnetic resonance imaging [MRI]) will also be submitted to an IRC for storage and will be available for evaluation by a central reader, if requested by the sponsor. Details for the collection and evaluation of radiographic images are included in the Radiology Manual provided to the study sites.

Tumor biopsy samples for NY-ESO-1 expression will be obtained from all subjects during the Pre-screening period as described in [Section 3.1.1](#) (either archival tumor tissue or a fresh biopsy sample). All subjects will provide peripheral blood samples for anti-NY-ESO-1 antibody assay at the screening visit for stratification.

Quality of life will be assessed up to 12 months from Day 1.

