	Prime Phase							Boost Phase	Follow-up	Follow-up
Visit	3	4	5	6	7	8	9	10+		
Timeline – Week(s)	1	3	5	7	9	11	13	Every 8 weeks ^b	Every 3 months until documentation of disease progression	Every 3 months for up to 5 years or until date of death
Timeline – Day(s)	1 ^a	22	36	50	64	78	92	Up to 1 year		
Allowed Visit Window - Days	+3	±3	±3	±3	±3	±3	±3	±7	±7	±14
Procedures										
Enrollment, stratification, and treatment allocation ^c	X									
Record prior and concomitant medications	X	X	X	X	X	X	X	X	X	X
Blood for central laboratory chemistry laboratory tests ^f	X	X		X	X		X			
Blood for central laboratory hematology ^f	X	X		X	X		X			
Urinalysis ^f	X						X			
Blood for anti-NY-ESO-1 plasma ELISA ^g	X						X			
Blood for immunity assessments ^g	X						X	X		
Blood for circulating tumor genomics ^h	X						X			
Pregnancy test ⁱ	X						X			
Vital sign measurements ^j	X	X	X	X	X	X	X	X		
Physical examination ^k	X	X	X	X	X	X	X	X		
12-lead electrocardiogram							X			
Tumor imaging with response assessment by RECIST v1.1 (CT scan or MRI) ^l					X			X	X	
ECOG Performance Status	X	X	X	X	X	X	X			
QoL assessment ^m	X						X	X		
Report AEs and SAEs ⁿ	X	X	X	X	X	X	X	X	X	X

	Treatment Period								Post-Treatment Period ^c	Long-term Follow-up Period ^d
	Prime Phase							Boost Phase	Follow-up	Follow-up
Visit	3	4	5	6	7	8	9	10+		
Timeline – Week(s)	1	3	5	7	9	11	13	Every 8 weeks ^b	Every 3 months until documentation of disease progression	Every 3 months for up to 5 years or until date of death
Timeline – Day(s)	1 ^a	22	36	50	64	78	92	Up to 1 year		
Allowed Visit Window - Days	+3	±3	±3	±3	±3	±3	±3	±7	±7	±14
Study drug administration: Placebo (Arm A) LV305 (Arm B)	X	X		X		X				
Study drug administration: Placebo (Arm A) G305 (Arm B)			X		X		X	X ^o		
Blood for LV305 persistence ^p							X	X	X	X
Tumor biopsy ^q							X			
Survival status ^r									X	X

AE = adverse event; CT = computed tomography; ECOG = Eastern Cooperative Oncology Group; IHC = immunohistochemistry; MRI = magnetic resonance imaging; NY-ESO-1 = New York esophageal squamous cell carcinoma-1; QoL = quality of life; RECIST = Response Evaluation Criteria in Solid Tumors; SAE = serious adverse event

- ^a Day 1 will occur within 28 days after the last dose of first-line systemic anti-cancer therapy or the last day of local regional therapy. Day 1 procedures must occur within 72 hours of randomization.

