- ^b In the Boost Phase, tumor imaging will be performed every 8 weeks for 1 year or until investigator-determined progressive disease, using RECIST v1.1, is documented.
- ^c The Post-treatment period will begin at the end of treatment and will continue until investigator-determined progressive disease, using RECIST v1.1, is documented. If a subject has reached 12 months on study without disease progression, tumor imaging will be performed every 12 weeks ±7 days until disease progression.
- ^d The Long-term Follow-up period will begin at the time investigator-determined progressive disease (using RECIST v1.1) is documented and will continue for up to 5 years, until the date of death, or until sponsor notification of study closure.
- ^e The following information must be available at Day 1: subjects must have documented completion of first-line systemic anti-cancer therapy and must have received at least 4 to 8 cycles of therapy (or no more than 180 days of systemic anti-cancer therapy); results of IHC testing for the presence of NY-ESO-1 (≥1% expression) must be available from the central laboratory; and the investigator-evaluated tumor response, using RECIST v1.1, to first-line systemic anti-cancer therapy must be documented.

- ^f During the study dosing period, all laboratory assessments are to be performed prior to dosing. Hematology and clinical chemistry samples will be shipped to the central laboratory for safety analyses, and will include: chemistry with liver function tests, lactate dehydrogenase, alkaline phosphatase, albumin, thyroid function, and hematology with complete blood count with differential. Urinalysis will be conducted at the central laboratories. All laboratory tests to be performed are listed in [Table 4](#).
- ^g Blood for anti-NY-ESO-1 T cell assessments to be collected only for subjects on prior to dosing on Day 1 and Day 92 only at select US sites. Additional blood samples for immunity assessments will be drawn for any subject who has no evidence of tumor progression by RECIST v1.1 at 1 year at the same select US sites.
- ^h For circulating tumor genomics, please see lab manual.

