- ⁱ For FCBP, serum and confirmation urine pregnancy testing will be performed by the local laboratory prior to dosing on Day 1; results must be negative. Serum pregnancy testing will be performed by the local laboratory prior to dosing on Day 92; results must be negative. Pregnancy testing will be performed more frequently as required per local regulatory authority.
- ^j Vital sign measurements will include body temperature, heart rate, respiratory rate, and resting systolic and diastolic blood pressure. On the day of each dosing, vital signs will be obtained no more than 60 minutes before dosing and 30 minutes after dosing (± 10 -minute window).
- ^k Once the Screening physical examination has been conducted, a simple symptom-directed physical examination should be performed for all subsequent visits. Measurements of body weight will be obtained at every visit.
- ^l Beginning in the Treatment period, imaging will be performed at 8-week intervals after Day 1 administration of the first dose of the study drug for up to 1 year or until the time investigator-determined progressive disease, using RECIST v1.1, is documented.
- ^m QoL assessments will be conducted at the study site. In addition to the screening QoL assessment, the QoL assessment will be obtained on Day 1 prior to the first dose of study drug, at Day 92, and at 6 months and 12 months after Day 1. All subjects, regardless of their disease response status, will continue to have QoL assessments performed for 12 months after Day 1.
- ⁿ All AEs and SAEs will be collected until 30 days after administration of the last dose of the study drug. Information on any SAEs and new malignancies that come to the attention of the site staff that are considered at least possibly related to CMB305 will be collected until the time of last subject contact.
- ^o After Day 92, G305 or placebo will be given on Day 148 and at 8-week intervals as a boost for up to 1 year, or until unacceptable toxicity, or investigator-determined progressive disease, using RECIST v1.1, is documented, whichever occurs first. AEs will be reported at the subsequent visit and until at least 30 days after the last dose.

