6.3 Efficacy Assessments

6.3.1 Tumor Imaging and Response

Subjects will have imaging performed at the time points stipulated in the schedule of events ([Table 1](#) and [Table 2](#)).

For individual subjects, the same imaging method should be used for all subsequent image collections throughout the study. The preferred method of imaging is via CT scan with intravenous (IV) contrast (MRI may also be considered as indicated). The slice thickness of images obtained at Pre-screening (i.e., after treatment with first-line systemic anti-cancer therapy), Screening, or while on study must be the same size or smaller than the slice thickness of the image obtained prior to administration of the first dose of first-line systemic anti-cancer therapy used to document all lesions present during staging of the synovial sarcoma. All images must include windows of the chest, abdomen, and pelvis. Brain images will be obtained if symptoms or signs suggest central nervous system involvement. Bone images will be obtained if symptoms, signs, or history suggest bone involvement by metastatic disease.

All images will be evaluated by the investigator using RECIST v1.1 measurement criteria expressed as PR, CR, SD, or PD (see [Appendix 1](#)).

Radiographic images (e.g., CT scan or MRI) will also be submitted to an IRC for storage and will be available for evaluation by a central reader, if requested by the sponsor. Subjects who have a tumor response of SD with evidence of $\geq 15\%$ to 20% increase in tumor burden will be submitted for evaluation by a central reader for adjudication.

The Radiology manual includes complete details for the collection, storage, and evaluation of images.

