6.3.1.3 Imaging During Treatment to the Time of Disease Progression

Tumor imaging assessments will be performed and evaluated every 8 weeks after Day 1 until investigator-determined PD (using RECIST v1.1) is documented. Disease progression will be assessed by the investigator using RECIST v1.1. For each subject, the images obtained during the Treatment period must have been collected using the same imaging method for all images during the Pre-screening and Screening periods. Subjects who have a global deterioration of health status that is attributed to progressive disease and leads to discontinuation of study treatment, but who are unable to provide radiographic evidence of disease progression (symptomatic deterioration), will be considered as having PD at the time of documented global deterioration of health for the purpose of determining PFS. Radiographic images (e.g., CT scan or MRI) will also be submitted to an IRC for storage and will be available for evaluation by a central reader, if requested by the sponsor. Details for the collection and evaluation of radiographic images are included in the Radiology Manual.

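### The scan schedule behind primary PFS is stated inconsistently, and SAP Table 3 does not say which calendar defines a missed assessment

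*Protocol*

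**What the plan says.** **Interval from Day 1.** Protocol Section 3.1.3: "Tumor imaging assessments will be performed every 8 weeks after Day 1". Section 6.3.1.3: "Tumor imaging assessments will be performed and evaluated every 8 weeks after Day 1 until investigator-determined PD (using RECIST v1.1) is documented". Footnote l to Table 2: "imaging will be performed at 8-week intervals after Day 1 administration of the first dose of the study drug for up to 1 year".

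**Table.** Section 6.3.1 sends sites to the table: "Subjects will have imaging performed at the time points stipulated in the schedule of events". In Table 2 of both documents, the imaging row that carries footnote l is marked at Visit 7 (Day 64, window ±3), at Visit 10+ and in the Post-Treatment column. No other Prime-phase visit is marked.

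**Boost phase.** Footnote b: "In the Boost Phase, tumor imaging will be performed every 8 weeks for 1 year or until investigator-determined progressive disease". It gives no starting day. The window for Visit 10+ is ±7 days in Table 2, whereas Section 3.3 gives ±3 days for every Treatment-period visit.

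**Early stoppers without progression.** Section 6.5.2 keeps subjects who stop for toxicity or withdraw from treatment in imaging follow-up. The Post-treatment period starts at the end of treatment (Section 3.1.4; SAP Section 8.1.1 counts it from last dose). The imaging mark in that column sits under "Every 3 months until documentation of disease progression". Footnote c moves imaging to every 12 weeks only after 12 months on study without progression.

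**Censoring.** SAP Table 3 censors progression or death that follows two or more missed assessments in a row, at the last adequate scan before the first missed one. It defines an adequate assessment but not a missed one.

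**The concern.** Scan dates fix the dates of radiographic progression, and investigator-assessed PFS is one of two primary endpoints. Its censoring rule counts missed scans, so it needs one calendar to count against. The documents offer more than one, and the SAP copies the table without choosing.

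The sharpest consequence is for subjects who stop dosing early. Someone who attends every scan that the Post-Treatment column asks for can be treated as having missed two. The same data then give an event on one stated schedule and a censored time on another. Early stopping can be related to treatment, so a scan interval or missed-scan count that changes with dosing status could in principle differ between arms.

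**Working it through.** **1. The plan's own figure.** Schoenfeld events for HR 0.55, one-sided alpha 0.0125, 90% power, 1:1: 4 × (2.241 + 1.282)² / (ln 0.55)² = 139, against 141 stated; 141 events give power 0.905. No scan day enters this formula, and the final PFS analysis is triggered by events, so the schedule does not alter it.

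**2. First scan.** Study day = 1 + 7 × weeks, so 8-weekly scans fall on Days 57, 113, 169, 225, 281 and 337. Day 64 is 9 weeks after Day 1 and its window is Days 61 to 67. Day 57 lies outside. So does Day 60, which is 8 weeks after a first dose given at the +3 limit (4 + 56). The column reading is sound: in the same table the G305 row falls on Days 36, 64 and 92, as in Section 5.2.

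**3. First Boost-phase scan.** The text rule gives Day 113. Counting 8 weeks from Day 64 gives Day 120.

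**4. Effect of Day 57 versus Day 64 on reported PFS.** Assume exponential PFS with the plan's placebo median of 4 months, HR 0.55, and progression recorded at the next scan. Recorded PFS at a landmark is S(last scan day before it), with S(d) = exp(−h·d/30.4375), h = ln 2/4 per month for placebo and 0.55 times that for CMB305.

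| Calendar | Placebo, 4/6/8/10 months | CMB305, 4/6/8/10 months |
|---|---|---|
| Days 57, 113, 169… | 52.6/38.2/27.8/20.2% | 70.2/58.9/49.4/41.5% |
| Days 64, 120, 176… | 50.5/36.7/26.7/19.4% | 68.7/57.6/48.4/40.6% |

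The largest gap is 52.6 − 50.5 = 2.1 points. These are upper bounds, because deaths and symptomatic deterioration are dated when they occur.

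**5. Early stoppers.** Take the nine scheduled dosing days from Day 22 to Day 260 as the last dose, with the first 3-monthly scan 91 days later. Under strict windows, 8-week day d is missed if d − 7 is after the previous scan and d + 7 is before the scan showing progression.

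| Last dose | First 3-month scan | 8-week days missed |
|---|---|---|
| 22 | 113 | 57 |
| 36 | 127 | 57, 113 |
| 50 | 141 | 57, 113 |
| 64 | 155 | 113 |
| 78 | 169 | 113 |
| 92 | 183 | 113, 169 |
| 148 | 239 | 169, 225 |
| 204 | 295 | 225, 281 |
| 260 | 351 | 281, 337 |

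Six of nine reach two missed scans; ±3 windows give the same count. If each scan is instead assigned to the nearest 8-week day, all nine have one missed scan and none is censored. (Day 141 is 28 days from both 113 and 169; this assigns it to 113.)

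Example following Table 2 throughout: scan on Day 64, last dose Day 92, progression on Day 183. On the 3-month column nothing was missed and this is an event. On the 8-week calendar, 113 − 7 = 106 is after 64 and 169 + 7 = 176 is before 183, so two scans are missed and the subject is censored at Day 64. A scan at the early end of that visit's own ±7 window (Day 176) would just count for Day 169.

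**6. Type I error.** Simulation under the null: 60,000 trials per scenario, 248 subjects, stated accrual, 8-weekly scans to Day 337 then 12-weekly, early stoppers' last dose drawn equally from the nine days and then 91-day scans, unstratified log-rank at 141 events; Monte Carlo SE about 0.0005. The early-stop shares are assumed.

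| Early stop, placebo/CMB305 | One-sided type I error, strict counting | Null HR |
|---|---|---|
| 5%/5% | 0.013 | 1.00 |
| 5%/10% | 0.014 | 0.99 |
| 5%/15% | 0.016 | 0.99 |
| 5%/25% | 0.021 | 0.97 |

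A repeat gave 0.014, 0.016 and 0.019 at 5/5, 5/15 and 5/25%. If only the scan interval differs and nobody is censored for it, the range is 0.012 to 0.015. Higher values (0.025 strict, 0.019 interval alone, at 5/25%) appear when progression-free subjects are censored at the data cutoff instead of the last scan, which is not the plan's rule.

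**The case against.** The best reply is that the footnotes already settle the early-stopper question. Footnote l belongs to the imaging row and makes no exception for stopped dosing. Footnote c belongs to the Post-Treatment column and relaxes imaging only after 12 months. Together they read as 8-weekly to 12 months and 12-weekly afterwards, and the 3-month heading covers several procedures besides imaging. This is the better reading, and it also reduces the conflict after 12 months between footnote c and Section 6.3.1.3 to wording. It does not remove the imaging mark under the 3-month heading, in a table to which sites are sent for their time points.

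The censoring count is also sensitive to inputs. With 84 days in place of 91 and ±7 windows it falls to 1 of 9 (Day 50), though with ±3 it stays at 6. That stands, and it shows that the answer depends on a counting rule nobody has written down. SAP Section 7.2 dates events by study day, which limits the effect of Day 57 versus Day 64 but does not define a missed scan. The competing-events analysis in SAP Section 8.2.2.2 leaves the same term undefined. The Radiology Manual may contain a calendar. It is not among these documents, and the counting rule for a primary endpoint belongs in the SAP.

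A reader might go further and take boost dosing visits as scan days, because footnote o says "After Day 92, G305 or placebo will be given on Day 148 and at 8-week intervals as a boost for up to 1 year". That would put the second scan on Day 148. No sentence ties scans to dosing, and the 12-week gap from Day 64 to Day 148 would contradict footnotes b and l. It is not evidence of harm.

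**Conclusion.** The inconsistency stands and should be corrected. Three parts matter: Day 57 against Day 64 ±3 for the first scan, with no printed first Boost-phase day; a 3-month column against 8-weekly footnotes for early stoppers; and no calendar or window for a missed assessment in SAP Table 3. The first shifts descriptive PFS rates by about 2 points at most. The second and third together leave the event or censored status of some early stoppers undecided.

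A reader might infer that the PFS test is compromised. The documents do not support that. Power and the 141-event basis are unchanged, and a calendar common to both arms has essentially no effect on the comparison. Type I error moves only slightly unless early stopping is clearly unequal: about 0.019 to 0.021 at an assumed 5% versus 25% with strict counting. The documents give no early-stopping rate, and these figures also rest on exponential PFS and an assumed even spread of last-dose days.

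**What to change.** Reconcile Table 2 in both documents, its footnotes b, c and l, and Protocol Sections 3.1.3, 3.3 and 6.3.1.3 into one explicit list of scan days with windows. Count it from Day 1, make it the same in both arms and independent of dosing status, and have it cover early discontinuation and the period after 12 months. The interval is for the sponsor to choose. In SAP Table 3, state that missed assessments are counted against that list, and how an out-of-window scan is assigned, including ties. Settle both before unblinding.

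The cost is a table correction in two documents and a short addition to SAP Table 3. Some scans may then fall between dosing visits.

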3.1.5 Long-term Follow-up Period

The Long-term Follow-up period will begin at the time investigator-determined PD (using RECIST v1.1) is documented and will continue for up to 5 years, until the date of death, or until sponsor notification of study closure.

Table 1 Schedule of Events for the Pre-Screening and Screening Periods

	Pre-Screening Period ^a	Screening Period ^b
Visit	1	2
Timeline – Day(s)	Day-180 to Day-29	Day -28 to Day -1
Procedures		
Informed consent/assent ^c	X	X
Obtain or collect tumor sample for IHC testing of NY-ESO-1 expression ^d	X	
Collect fresh tumor sample to assess tumor biomarkers (frozen and FFPE) at select U.S. sites		X
Investigator review of tumor response to first-line systemic anti-cancer therapy using RECIST v1.1 ^e	X	
Obtain images collected at the standard-of-care time point for the first evaluation of response to first-line systemic anti-cancer therapy ^f	X	
Tumor imaging (CT/MRI) for baseline tumor response assessment ^g		X
Inclusion and exclusion criteria		X
Demographics and medical history		X
Tumor-specific therapy history		X
Record prior and concomitant medications		X
Blood for chemistry laboratory tests ^h		X
Blood for hematology laboratory tests ^h		X
Blood for coagulation tests laboratory tests ^h		X
HIV, hepatitis B (HepB), and hepatitis C (HepC) tests ^h		X
Blood for anti-NY-ESO-1 plasma ELISA ⁱ		X
Blood for circulating tumor genomics ^j		X
Urinalysis ^h		X
Pregnancy test ^k		X
Vital sign measurements ^l		X
Physical examination ^m		X
12-lead electrocardiogram		X
ECOG		X
QoL assessment		X
Blood for LV305 persistence		X

CT = computed tomography; ECOG = Eastern Cooperative Oncology Group; ELISA = Enzyme-linked immunosorbent assay; HIV = human immunodeficiency virus; ICF = informed consent form; IHC = immunohistochemistry; MRI = magnetic resonance imaging; NY-ESO-1 = New York esophageal squamous cell carcinoma-1; QoL = quality of life; RECIST = Response Evaluation Criteria in Solid Tumors

^a The Pre-screening period is up to 151 days (Day -180 to Day -29) and is the time from the subject and/or their legally authorized representative signing the Pre-screening ICF/assent form to the time of signing the Main study ICF/assent form. The Pre-Screening can commence at any time after first dose of first-line systemic anti-cancer therapy.

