6.5 Removal of Subjects from the Trial or Study Drug

Unless consent is withdrawn and the subject is unwilling to continue with safety follow-up, the subject is lost to follow-up, or the study is terminated, all efforts should be made to continue tumor and quality of life assessments as well as safety monitoring of all subjects.

Subjects who withdraw prior to the end of the study should be followed for new AEs for at least until 30 days after their last dose of study drug, i.e., CMB305. If the subject withdraws prematurely and is unwilling to continue safety follow-up, any subsequent SAE that may be causally related to study drug (i.e., CMB305) that comes to the attention of the site staff should be reported to IMDZ.

Information for long-term survival status should be obtained by any means, which includes, but is not limited to, public records where allowed by local authority, telephone contact, during an in-clinic visit, chart review, or via communicating with an individual (e.g., family, friend, referring health care provider) who is knowledgeable of the subject's survival status. More frequent survival status updates may be obtained at the request of the sponsor.

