6.5.2 Removal from Study Drug

While subjects will be encouraged to continue participation in the study for safety and survival follow-up, subjects **MUST** be discontinued from receiving further study drug for the following reason:

- Progressive disease by RECIST v1.1 criteria
- Withdrawal of informed consent from study treatment
 - Subject will continue to be followed for imaging and quality-of-life assessment
- Any clinical AE that meets treatment discontinuation criteria in section 5.6 or any other reason that, in the opinion of the investigator, indicates that continued dosing on the study is not in the best interest of the subject
 - Subject will continue to be followed for imaging and quality-of-life assessment

Subjects will be permitted to continue study drug if the RECIST v1.1 criteria for PD are met provided they meet all the following criteria:

- Evidence of clinical benefit as assessed by the investigator
- Absence of symptoms and signs (including worsening of laboratory values) indicating unequivocal progression of disease
- No decline in ECOG performance status that can be attributed to disease progression
- Absence of tumor growth at critical anatomical sites (e.g., leptomeningeal disease) that cannot be managed by protocol-allowed medical interventions
- Subjects for whom approved therapies exist must provide written consent to acknowledge deferring these treatment options in favor of continuing study treatment at the time of initial apparent progression. Study treatment will be discontinued upon commencement of subsequent systemic anti-tumor therapy.

No unblinding will be permitted for subjects who continue study treatment beyond progression.

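### Table 2 leaves quality of life (QoL) unmarked after treatment ends or disease progresses, although its own footnote m requires QoL in every subject to month 12

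*Protocol*

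**What the plan says.** **Text that continues QoL.** Protocol Table 2, footnote m, sets QoL at screening, Day 1, Day 92 and 6 and 12 months after Day 1, completed at the site. It adds: "All subjects, regardless of their disease response status, will continue to have QoL assessments performed for 12 months after Day 1". SAP Table 2 repeats the footnote. The protocol synopsis and Section 3.1.3 set QoL to 12 months from Day 1 with no limit at progression. Section 6.5 says that, apart from withdrawn consent with refusal of safety follow-up, loss to follow-up or study termination, "all efforts should be made to continue tumor and quality of life assessments as well as safety monitoring of all subjects".

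**The grid.** In the Table 2 row labelled "QoL assessment ^m" the marks stand at Day 1, Day 92 and the Boost Phase. The Post-treatment and Long-term Follow-up cells are empty, in both documents. A subject changes column at progression: "The Long-term Follow-up period will begin at the time investigator-determined progressive disease (using RECIST v1.1) is documented".

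**Section 6.5.2.** The bullet "Progressive disease by RECIST v1.1 criteria" has no follow-up text beneath it. The bullets for withdrawal of consent to treatment and for adverse events or other reasons each carry: "Subject will continue to be followed for imaging and quality-of-life assessment".

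**Analysis.** SAP 8.2.3.4 names pattern mixture models for EQ-5D-5L and gives example code for a mixed model for repeated measures. SAP 7.2 does not impute missing efficacy data unless otherwise specified.

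**The concern.** The grid and its footnote give different answers for a subject who has left treatment. The blanks do not look like a layout habit, because concomitant medications, adverse events, LV305 persistence and survival status are all marked in both follow-up columns. The blank Post-treatment cell also conflicts with 6.5.2, which continues QoL after adverse-event removal or withdrawal from treatment. The gap is therefore wider than progression.

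If a site schedules from the grid, QoL is not collected after treatment ends or disease progresses. The month 6 and month 12 comparisons would then rest on subjects who are still progression-free, a group selected by an outcome that treatment is meant to change. If CMB305 delays progression, the selection differs by arm.

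**Working it through.** **Inputs** (Protocol 7.1, SAP 4): 124 subjects per arm; placebo median PFS 4 months, HR 0.55; placebo median OS 20 months, HR 0.59; 1-sided alpha 0.0125; 90% power. The documents give no QoL completion rate. Exponential PFS and OS, no other dropout and no treatment past progression are assumptions made here.

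**Step 1. The plan's own figures.** Events by Schoenfeld = 4(z₀.₉₈₇₅ + z₀.₉₀)² / (ln HR)².
- PFS: 4(2.241 + 1.282)² / (ln 0.55)² gives 139, against 141 stated. Power at 141 events is 90.5%.
- OS: the same formula with HR 0.59 gives 179, as stated. Power is 90.1%.

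**Step 2. Forms available at month t.** If the grid is followed, a form needs the subject to be progression-free: 0.5^(t/4) for placebo and 0.5^(0.55t/4) for CMB305. If footnote m is followed, the subject need only be alive: 0.5^(t/20) and 0.5^(0.59t/20).

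| Time | Grid: placebo | Grid: CMB305 | Footnote m: placebo | Footnote m: CMB305 |
|---|---|---|---|---|
| Day 92 | 60% (74) | 75% (93) | 90% (112) | 94% (117) |
| Month 6 | 35% (44) | 56% (70) | 81% (101) | 88% (110) |
| Month 12 | 12.5% (15.5) | 32% (39.5) | 66% (81.8) | 78% (97.0) |

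Of all randomised subjects, the grid reading loses 33% at Day 92, 54% at month 6 and 78% at month 12. Part of that is death, which no schedule can repair. Among those alive at month 12 the grid keeps (15.5 + 39.5) / (81.8 + 97.0) = 55.0 / 178.8 = 31%, so 69% of the obtainable forms are lost.

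**Step 3. Sensitivity.** Protocol 3.2 cites PFS of 6 to 8 months after initial response to first-line therapy. With HR 0.55 and OS unchanged:
- Placebo median 6 months: 31.0 and 57.8 forms at month 12. That is a 64% loss of all randomised, or (178.8 − 88.8) / 178.8 = 50% of those alive.
- Placebo median 8 months: 43.8 and 70.0 forms. That is a 54% loss of all randomised, or (178.8 − 113.8) / 178.8 = 36% of those alive.
- Placebo median 4 months with PFS HR 1.0: 15.5 forms in each arm, an 87.5% loss with no imbalance.

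**Step 4. Precision at month 12.** SE = SD × √(1/n₀ + 1/n₁). The root is 0.300 for 15.5 and 39.5 forms and 0.150 for 81.8 and 97.0, so the SE doubles whatever the SD. At an assumed SD of 0.25 it goes from 0.038 to 0.075.

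**Step 5. Visits.** Boost visits fall on Days 148, 204, 260, 316 and 372, ±7 days in Table 2. Month 6 is 6 × 30.4375 = 182.6 days, about Day 183. It lies between the windows 141–155 and 197–211, so it falls in none. Month 12, about Day 365, touches only the lower edge of Day 372 ± 7.

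**The case against.** **The row cannot be read without its footnote.** Only footnote m turns the Boost mark into months 6 and 12. Table 2 also uses footnotes to extend rows elsewhere: the biopsy row marks Day 92, and footnote q adds Day 365 and progression. Every text statement on QoL duration agrees with footnote m. This stands. The intent is clear, and the loss is conditional on sites following the grid.

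**A reader might infer that 6.5.2 stops QoL at progression.** It does not. It is silent there, and its parent Section 6.5 continues QoL in all subjects. A missing sub-bullet is not a stop rule.

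**A reader might infer that a progressed subject has no visit at which to complete a form.** Long-term Follow-up contacts occur every 3 months, ±14 days. Footnote p calls for persistence blood at 6 to 9 months and at 12 to 15 months after Day 1, and that row is marked in both follow-up columns. Usable contacts exist. What is missing is a QoL mark and a window tied to months 6 and 12.

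**Progression does not always end treatment visits.** Section 6.5.2 states: "Subjects will be permitted to continue study drug if the RECIST v1.1 criteria for PD are met", subject to conditions. The counts in the working ignore this and so overstate the loss. Treatment stopped for other reasons would work in the opposite direction.

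**The SAP names pattern mixture models.** This class of method suits outcome-related missingness. However, the SAP defines no patterns and no identifying restrictions, and its code has no term for progression. If no post-progression form exists, that part of the model must be supplied by assumption.

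**QoL is a lesser endpoint.** It is secondary, has no power statement, and lies outside the controlled TTNT-then-DMFS sequence (Protocol 7.7.2, SAP 8.2.3). This stands and limits the consequence.

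**Conclusion.** The contradiction between the grid and footnote m is real and appears in both documents. The grid is the outlier. Section 6.5.2 leaves a gap under progressive disease but does not contradict the footnote.

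To the extent that sites follow the grid, post-treatment and post-progression QoL is lost by schedule and cannot be recovered later. At the limit where all do, the month 12 comparison would use about 16 placebo and 40 CMB305 subjects instead of about 82 and 97, and its standard error would double. These counts rest on the plan's PFS and OS figures, exponential times, no other dropout and no treatment past progression.

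The documents do not support saying that the trial will lose most of its QoL data, or that the loss must differ by arm. The first needs sites to set aside an explicit footnote, and the second needs a PFS effect. At Day 92 even the grid reading loses only a third. The primary endpoints are untouched. The correction is worth making because it is nearly free and protects a secondary comparison from selection by outcome.

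**What to change.** 1. In Table 2 of the protocol and of the SAP, mark QoL at months 6 and 12 after Day 1 in the Post-treatment and Long-term Follow-up columns.
2. In footnote m, state a window for month 6 and for month 12 that also covers subjects still on treatment, since month 6 falls in no Boost window.
3. In Protocol 6.5.2, add under the progressive-disease bullet that QoL continues to 12 months after Day 1, in line with footnote m and Section 6.5.

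The cost is wording in two documents. Footnote m already requires the assessments, so the design does not change. Subjects who have left treatment complete at most two further questionnaires, which can be combined with the existing follow-up or persistence-blood contacts.
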